The literature on opioid dependence has consistently demonstrated elevated levels of cortisol (12, 25-38) and catecholamines (12, 39-43) during the acute withdrawal phase. Human and animal

models postulate that long-term use of opioids induces hypoadrenalism through impairment of the hypothalamic-pituitary-adrenal (HPA) axis. Opioid withdrawal leads to marked elevations of cortisol as a result of excess ACTH secretion (26, 32, 35). This HPA activation persists following normalization of the adrenergic system, which led some authors to conclude that cortisol is a more sensitive indicator of opioid withdrawal than catecholamines (30, 32). A small study by Higgins et al. on 5 non-dependent subjects assessed acute opioid withdrawal after a single dose of morphine and observed a dose-dependent increase in cortisol levels when subjects were subsequently injected with naloxone (28). Despite the clinical relevance, several limitations reduce the applicability of those results to our study population, mainly the selection of opioid-dependent subjects and rapid induction of withdrawal – through injection of naloxone or abrupt cessation of opioid with support medications such as alpha₂-agonists. Since our subjects are mostly opioid-naive prior to hospitalization and will be gradually weaned off their opioids, the magnitude of increase in cortisol levels will likely be lower.

As for catecholamines, serum epinephrine and norepinephrine appear to increase rapidly following opioid withdrawal in numerous animal and human studies (12, 39-43). However, in contrast with cortisol, catecholamine levels decrease shortly following acute withdrawal. In a study of subjects undergoing rapid opioid detoxification, catecholamine levels peaked two hours following naloxone administration (12). A gradual opioid weaning as often seen in clinical practice is unlikely to be recognized through measurement of serum catecholamines.

3. Research objectives

Research question

What are the signs and symptoms of opioid-associated iatrogenic withdrawal syndrome (OIWS) in the adult ICU population?

Primary objective

To identify specific signs and symptoms of OIWS in mechanically ventilated adult ICU patients receiving at least 72 hours of regular opioids at the Montreal General Hospital (MGH) and the Royal Victoria Hospital (RVH) from February to October 2018

Secondary objective

To determine if the presence of OIWS is associated with an increase in serum cortisol.

4. Methods

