4.4 Definition of variables

4.4.1 Primary outcome variables

Dependent variables

- Presence of signs and symptoms of OIWS
 - According to daily evaluation by investigator after an episode of opioid weaning has begun (See Appendix III)

Independent variables

- **Presence of OIWS** (qualitative nominal - dichotomous)
 - According to DSM-5 evaluation completed daily by physician after an episode of opioid weaning has begun
- **Demographic and clinical variables**
 - **Age** (quantitative continuous): Age in years at ICU admission
 - **Sex** (qualitative nominal - dichotomous)
 - **Weight** (quantitative continuous): Weight in kg at ICU admission
 - **Height** (quantitative continuous): Height in cm at ICU admission
 - **Body mass index (BMI)** (quantitative continuous): In kg/m² at ICU admission
 - **Ethnicity** (qualitative nominal)
 - **Site of ICU admission** (qualitative nominal - dichotomous)
 - **Smoking status** (qualitative nominal - dichotomous)
 - Number of cigarettes per day according to medical chart, patient or family at ICU admission (quantitative discrete)
 - Number of pack-years according to medical chart, patient or family at ICU admission (quantitative continuous)
 - **Principal diagnosis at ICU admission** (qualitative nominal)
 - Definite diagnosis according to medical chart at ICU admission using ICD-10 classification
 - **Length of stay in the ICU** (quantitative continuous)
 - Time in hours from ICU admission to ICU discharge, transfer to ward or patient death, according to medical chart
 - Opioid withdrawal has been associated with longer ICU stays (4-6)
 - **Duration of mechanical ventilation** (quantitative continuous)

- Time in hours according to medical chart
- Longer duration of mechanical ventilation has been associated with increased risk of IWS in ICU patients (7)
- **Acute Physiology and Chronic Health Evaluation II Score (APACHE II)** (qualitative ordinal)
 - To assess severity of disease and ICU mortality on a scale of 0 to 71 (47)
 - As reported by an archivist based on data from the first 24 hours of ICU admission
- **Glasgow Coma Scale (GCS)** (qualitative ordinal)
 - To assess mental status and severity of brain injury on a scale of 3 to 15 (48)
 - As reported by nurse on patient flow sheet at ICU admission
- **Renal function**
 - Daily serum creatinine in $\mu\text{mol/L}$ according to medical chart (quantitative continuous)

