4.5 Data collection and study procedure (Appendix II)

From February to October 2018, patients from the MGH and RVH critical care units will be screened daily from unit patient lists generated through Oasis for eligibility. The investigators will be transiting daily between both centers. Once a patient is approaching 72 hours of mechanical ventilation and regular opioid administration, subjects will be evaluated for inclusion and exclusion criteria according to medical chart, and data will be recorded in the "Patient Screen Log". Once a patient fits our entry criteria, here are the steps for obtaining consent:

1- A member of the treating team (ICU physician or patient nurse) will inform the patient about this research project. If the patient is deemed unfit to provide informed consent, the patient's decision maker will be approached.

2- If patient/decision maker shows interest, a member of the research team, independent of the clinical care of the patient will meet with the patient/decision maker and explain the research and seek informed consent.

3- If the intubated patient verbally agrees but is unable to sign the consent, then a witness will sign the consent and the discussion will be documented on the consent form.

4- If the consent is obtained from a decision maker, then we will further seek direct patient consent as soon as patient is deemed apt to consent.

In this case, we would ask the patient to sign a new consent form and a copy will be provided to the patient and the newly signed consent will be kept in our files.

Once recruitment is completed, the patient will be given a subject number and placed on the "Enrollment List", which includes medical record numbers, admission dates, screen dates and enrollment dates.

After enrollment, demographic, reason for admission, lifestyle and medical data will be collected retrospectively from the medical chart, the patient's family and the medical team, and will be noted in the "Enrollment and Outcomes Form". The reasons for exclusion and the number of patients who refused consent will be collected. Temporarily excluded patients will be re-evaluated daily for possible inclusion into the study.

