Once the patient begins the targeted opioid weaning of $\geq 10\%$, investigators will perform evaluations daily between 10am and 2pm. These evaluations will consist of using pre-tested data collection sheets to record signs and symptoms of possible OIWS, opioid doses, administered medications, laboratory values and other clinical data such as the RASS, CPOT and CAM-ICU scores. Data collection will be based on subject observation and interview when possible, nurse assessments, medical charts and laboratory results. Serum cortisol levels will be measured on the first day of opioid weaning (± 2 hours from dose decrease) and on the day patient is transferred to the ward or 72 hours from start of weaning whichever occurs first.

Once a weaning episode is identified, the physician collaborator will be contacted to perform daily DSM-5 evaluations. DSM-5 evaluations will be placed in opaque envelopes and investigators will be blinded to the results throughout the study. Additionally, for each patient, at least one inter-rater DSM-5 evaluation between 2 physician collaborators will be performed in order to assess interrater reliability. The two evaluations will be done within 2 hours of each other to minimize time-related discrepancies.

If opioid weaning is unsuccessful and opioid dose is re-increased, the subject will continue to be observed, however daily evaluations will only resume at the next weaning episode. Daily follow-up ends on day of transfer to the ward. One additional data collection and DSM-5 evaluation will be performed on the same day within 24 to 96 hours following transfer. Follow up ends 14 days after initial opioid weaning if patient remains in the ICU or if patient dies.

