Dermatologic symptoms	Mottling	Presence of violaceous marbled discoloration of the skin during evaluation or according to nurse assessment in the previous 24h	Qualitative nominal (dichotomous)
	Piloerection	Presence during evaluation or according to nurse assessment in the previous 24h	Qualitative nominal (dichotomous)
	Sweating	Presence without apparent reason (not caused by room temperature) during evaluation or according to nurse assessment in the previous 24h	Qualitative nominal (dichotomous)
Musculoskeletal symptoms	Bone, joint or muscle aches	Presence during evaluation or according to nurse assessment in the previous 24h	Qualitative nominal (dichotomous)
	Muscle cramps	Presence during evaluation or according to nurse assessment in the previous 24h	Qualitative nominal (dichotomous)
	Muscle tone	Presence during evaluation or according to nurse assessment in the previous 24h	Qualitative nominal (dichotomous)

		(e.g. clenching wrists and toes, hunched shoulders, abnormal tense position of head, arm or legs)	
	Uncoordinated/ repetitive movement	Presence of involuntary movements of arm and/or legs, muscle twitches, during evaluation or according to nurse assessment in the previous 24h	Qualitative nominal (dichotomous)

^a Previous 24h designate the interval between midnight of the previous day and midnight of the day on which evaluation of the signs and symptoms occurs. A fixed time frame was chosen to standardize collection of signs and symptoms.

^b Nurse assessment comprises written (i.e. notes in medical chart or patient flow sheet) and/or verbal communication.

^c On the day of transfer, patients will be evaluated from midnight of the previous day until time of evaluation. Following transfer to ward, patients will be evaluated from midnight of the current day to time of evaluation.

Appendix IV. Diagnostic and Statistical Manual of Mental Diagnosis-V (DSM-5): “Opioid Withdrawal” criteria.

Diagnostic criteria:

A. Presence of either of the following;

1. Cessation of (or reduction in) opioid use that has been heavy and prolonged (i.e., several weeks or longer).
2. Administration of an opioid antagonist after a period of opioid use.

B. Three (or more) of the following developing within minutes to several days after

1. Dysphoric mood.
2. Nausea or vomiting.
3. Muscle aches.
4. Lacrimation or rhinorrhea.
5. Pupillary dilation, piloerection, or sweating.
6. Yawning.
7. Fever.
8. Insomnia.

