C. The signs or symptoms in Criterion B cause clinically significant distress or impairment in social, occupational, or other important areas of functioning.

D. The signs or symptoms are not attributable to another medical condition and are not better explained by another mental disorder, including intoxication or withdrawal from another substance.

Reference: Association AP. Diagnostic and Statistical Manual of Mental Disorders: DSM-5. 5th ed. Washington, DC: American Psychiatric Publishing; 2013.

Appendix V. Acute Physiology and Chronic Health Evaluation II (APACHE II) developed by Knaus et al.

PHYSIOLOGIC VARIABLE	HIGH ABNORMAL RANGE					LOW ABNORMAL RANGE			
	+4	+3	+2	+1	0	+1	+2	+3	+4
TEMPERATURE — rectal (°C)	≥ 41*	39*–40.9*		38.5*–38.9*	36*–38.4*	34*–35.9*	32*–33.9*	30*–31.9*	≤ 29.9*
MEAN ARTERIAL PRESSURE — mm Hg	≥ 160	130–159	110–129		70–109		50–69		≤ 49
HEART RATE (ventricular response)	≥ 180	140–179	110–139		70–109		55–69	40–54	≤ 39
RESPIRATORY RATE — (non-ventilated or ventilated)	≥ 50	35–49		25–34	12–24	10–11	6–9		≤ 5
OXYGENATION: A-aDO ₂ or PaO ₂ (mm Hg)									
a. FIO ₂ ≥ 0.5 record A-aDO ₂	≥ 500	350–499	200–349		< 200				
b. FIO ₂ < 0.5 record only PaO ₂					PO ₂ > 70	PO ₂ 61–70	PO ₂ 55–60	PO ₂ < 55	
ARTERIAL pH	≥ 7.7	7.6–7.69		7.5–7.59	7.33–7.49		7.25–7.32	7.15–7.24	< 7.15
SERUM SODIUM (mMol/L)	≥ 180	160–179	155–159	150–154	130–149		120–129	111–119	≤ 110
SERUM POTASSIUM (mMol/L)	≥ 7	6.6–9		5.5–5.9	3.5–5.4	3–3.4	2.5–2.9		< 2.5
SERUM CREATININE (mg/100 ml) (Double point score for acute renal failure)	≥ 3.5	2–3.4	1.5–1.9		0.6–1.4		< 0.6		
HEMATOCRIT (%)	≥ 60		50–59.9	46–49.9	30–45.9		20–29.9		< 20
WHITE BLOOD COUNT (total/mm ³) (in 1,000s)	≥ 40		20–39.9	15–19.9	3–14.9		1–2.9		< 1
GLASGOW COMA SCORE (GCS): Score = 15 minus actual GCS									
A Total ACUTE PHYSIOLOGY SCORE (APS): Sum of the 12 individual variable points									
Serum HCO ₃ (venous-mMol/L) [Not preferred, use if no ABGs]	≥ 52	41–51.9		32–40.9	22–31.9		18–21.9	15–17.9	< 15

B AGE POINTS:
Assign points to age as follows:

AGE(yrs)	Points
≤ 44	0
45–54	2
55–64	3
65–74	5
≥ 75	6

C CHRONIC HEALTH POINTS

If the patient has a history of severe organ system insufficiency or is immuno-compromised assign points as follows:
a. for nonoperative or emergency postoperative patients — 5 points
or
b. for elective postoperative patients — 2 points

DEFINITIONS

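### No pre-wean baseline is designated for the Appendix III signs, so the W+ versus W- comparison cannot separate signs that appear during weaning from signs that were already there

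*Combined protocol and SAP*

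**What the plan says.** Section 3 sets the aim: "To identify specific signs and symptoms of OIWS in mechanically ventilated adult ICU patients". Section 4.4.1 defines the dependent variable, presence of signs and symptoms, as "According to daily evaluation by investigator after an episode of opioid weaning has begun". The grouping variable, presence of OIWS, comes from a separate source: "According to DSM-5 evaluation completed daily by physician after an episode of opioid weaning has begun".

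Under section 4.5, once weaning starts, "investigators will perform evaluations daily between 10am and 2pm". For items that look back over the previous 24 hours, Appendix III footnote a fixes the window as "the interval between midnight of the previous day and midnight of the day on which evaluation of the signs and symptoms occurs", that is, the calendar day before the evaluation.

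Section 5.1.1 makes each DSM-5-evaluated day an episode. It classes a patient as W+ if any day is positive and W- otherwise, tallies each sign per episode, and compares proportions between the groups. It contains no change from baseline, no definition of new onset, and no rule for using the confounders listed in 4.4.1. Only cortisol (4.4.2) has a basal value and a within-patient change.

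**The concern.** Many Appendix III items (temperature, heart rate, blood pressure, respiratory rate, suctioning, stools, agitation) can be abnormal in a ventilated patient for reasons unrelated to opioids. If the tally records presence only, a sign that has persisted since admission counts the same as one that appeared after the dose fell. The study is meant to prepare the ground for a bedside screening tool (4.1), so the signs it puts forward matter. A common illness sign could look characteristic of withdrawal because the W+ patients were sicker, or a real withdrawal sign could be hidden by a high background.

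The plan gives reasons to expect unequal background. Section 2 lists ARDS and higher daily opioid and benzodiazepine doses as adult risk factors for IWS. Section 4.4.1 links IWS to longer ventilation, higher cumulative opioid dose and longer opioid exposure. Severity is measured by APACHE II from the first 24 hours in the ICU, not near the wean.

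**Working it through.** The plan has no figure of its own to reproduce on this point: it gives no sign prevalences, and the target of 50 (5.2) is a feasibility count. The prevalences below are assumptions, shown over a range.

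**1. What the first look-back window covers.** Inputs: evaluation between 10:00 and 14:00 (4.5); window equal to the preceding calendar day (Appendix III, footnote a).
- Wean starts before that day's evaluation: the window closed at midnight, so 24/24 = 100% of it is pre-wean. It is still attached to that day's DSM-5 result and tallied.
- Wean starts after that day's evaluation: the first sheet is the next day's, and its window is the wean day itself. The pre-wean share is at least 10/24 = 42% (evaluation at 10:00) or 14/24 = 58% (evaluation at 14:00).

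**2. Equal background.** Let b be the probability that a sign is already present, the same in both groups, and w the probability that withdrawal produces it in a patient without it. Then W+ = 1 − (1 − b)(1 − w), W- = b, and the difference is w(1 − b). With w = 0.30:

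| b | W+ | W- | Difference | Share of W+ tally already present, b/W+ |
|---|---|---|---|---|
| 10% | 37% | 10% | 27 points | 27% |
| 30% | 51% | 30% | 21 points | 59% |
| 50% | 65% | 50% | 15 points | 77% |
| 70% | 79% | 70% | 9 points | 89% |

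With no background the difference would be 30 points. With w = 0 it is 0 in every row, so equal background creates no false sign.

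**3. Unequal background, no withdrawal effect (w = 0).** The difference is b in W+ minus b in W-:
- 40% v 30%: 10 points
- 50% v 30%: 20 points
- 60% v 30%: 30 points

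Nothing in the planned tally would distinguish these from a withdrawal effect.

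**4. What a baseline recovers.** If background signs persist unchanged from the baseline day, new onset among W+ patients without the sign at baseline is (W+ − b)/(1 − b). For b = 50% this is (0.65 − 0.50)/0.50 = 0.30, which is w; the other rows give the same. In step 3 it is 0 in both groups.

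**5. Whether adjustment could do the job instead.** Applying the single prospective adult incidence quoted in section 1 to the target gives 50 × 0.167 = 8.35, so about 8 W+ patients. That is too few to adjust for the many covariates in 4.4.1.

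**The case against.** A reader might infer that pre-existing signs are simply counted as signs of OIWS. The documents do not support that. OIWS is assigned by a physician's DSM-5 evaluation, to which the investigators are blinded. Appendix IV requires an onset, "Three (or more) of the following developing within minutes to several days after", and an attribution: "The signs or symptoms are not attributable to another medical condition and are not better explained by another mental disorder". This protects the W+ label. It does not filter the investigators' separate tally, which asks mostly for presence and includes items outside criterion B as reproduced there (heart rate, blood pressure, respiratory rate, suctioning, agitation, tremor).

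A reader might also infer that no pre-wean value exists. That goes too far: step 1 shows that the first sheet may already describe the whole day before the wean. What is missing is any instruction to treat it as baseline.

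Nor is the contrast necessarily biased. W- patients are weaned too and carry background signs, so bias requires background to differ. The last column of the table describes what the W+ proportion is made of; it does not measure bias.

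The plan does record infection-related fever, *C. difficile* or feed-related diarrhea, pain, delirium and benzodiazepines. Its sweating and seizure definitions exclude some other causes, several mimics are excluded at entry, and section 6.2 admits confounding and a mainly descriptive purpose. These points stand, but section 5.1 says nothing on how the recorded confounders enter the tally, and 6.2 does not mention the missing baseline.

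Finally, a pre-wean day is spent at full opioid dose and is not a neutral reference. That is correct and limits how the new measure should be read.

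**Conclusion.** The point holds in a limited form. As planned, the primary comparison cannot separate persisting from new signs, and some first-day records tallied as weaning episodes may describe only hours before weaning. The reported W+ proportions will include background. The contrast shrinks by the factor (1 − b) when background is equal, and shifts by the background gap when it is not: 10 to 30 points over the assumed range, 20 points at 50% v 30%. Those sizes rest on assumed prevalences. The direction does not, although bias requires unequal background, which the plan's own risk factors make plausible but do not establish. This is a worthwhile, inexpensive improvement to a descriptive study. It does not show that the DSM-5 classification is wrong or that the study cannot meet its aim.

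**What to change.** In 4.5, designate the last full calendar day before the first wean as baseline for the chart-derived Appendix III items. Where the first sheet's look-back already covers that day, use it; otherwise extract it from the chart. Screening begins at a suitable time ("Once a patient is approaching 72 hours of mechanical ventilation and regular opioid administration"), and 4.5 already provides for retrospective chart collection after enrollment.

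In 5.1.1:
- Do not tally 24-hour items from a wholly pre-wean window as a weaning episode.
- Keep the planned prevalence by W+ and W-.
- Beside it, report each sign as new or worse than baseline, stating the denominator. For continuous items without a presence cut-off, such as heart rate, blood pressure and respiratory rate, report the change from baseline.

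The cost is at most one extra sheet per patient, so about 50, with no added bedside visit and nothing removed from the plan. There are two downsides to state. Interview-only and bedside-only items, such as startle and time to regain calm, will have no baseline. And because baseline is at full opioid dose, signs that opioids suppress (pupil size, RASS) may appear new in both groups, so the new-or-worse measure should be read as a W+ versus W- contrast and not as a rate in W+ alone.

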5.1 Statistical analysis

5.1.1 Descriptive statistics

Demographic and clinical characteristics of patients who developed OIWS will be compared to those who did not. Categorical variables will be presented as proportions. For continuous variables, means and standard deviations will be computed for normal distributions whereas medians (interquartile range) will be used for non-normal distributions.

For the primary outcome, episodes will be compared between the withdrawal positive (W+) group and the withdrawal negative (W-) group. Every day on which the DSM-5 is positive is equivalent to an episode of withdrawal, whereas a negative DSM-5 counts as an episode in which no withdrawal was observed. Patients who are positive for at least one episode of withdrawal make up the W+ group, whereas those who did not have a single episode of withdrawal make up the W- group, thus eliminating crossover. If a single patient experiences multiple days of withdrawal, s/he will account for multiple episodes in the study. Signs and symptoms will be tallied per episode and compared between the two groups. The results will be presented as proportions (i.e. incidence of symptom per total episodes). In the event of a discordant inter-rater evaluation, only the positive result will be taken into account.

For the secondary outcome, serum cortisol levels and changes in serum cortisol levels are continuous variables and therefore descriptive statistics will be used as stated above, depending on the distribution.

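### Comparing total ICU stay and total ventilation time between ever- and never-OIWS patients can be biased toward longer times in W+, because longer-staying patients are rated more often

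*Combined protocol and SAP*

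**What the plan says.** Section 4.4.1 places ICU length of stay and duration of mechanical ventilation among the demographic and clinical variables. Stay is "Time in hours from ICU admission to ICU discharge, transfer to ward or patient death, according to medical chart". Ventilation is a total in hours from the chart. Neither is cut at the start of weaning.

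The notes beside them point in opposite directions. For stay the plan remarks "Opioid withdrawal has been associated with longer ICU stays", which treats it as a consequence. Ventilation is described as a risk factor for withdrawal.

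Section 5.1.1 states: "Demographic and clinical characteristics of patients who developed OIWS will be compared to those who did not". It assigns groups over the whole follow-up: "Patients who are positive for at least one episode of withdrawal make up the W+ group", and W- patients have no positive day.

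OIWS status is determined "According to DSM-5 evaluation completed daily by physician after an episode of opioid weaning has begun" (section 4.4.1). Under section 4.5, "Daily follow-up ends on day of transfer to the ward". One further rating follows 24 to 96 hours after transfer, and follow-up stops at 14 days for patients still in the ICU. The plan sets no landmark, no time-dependent OIWS status and no allowance for the number of days rated.

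**The concern.** Each extra ICU day after weaning normally adds a rating, and one positive rating is enough to make a patient W+. Group membership therefore depends partly on the quantity being compared. Days in the ICU before the first positive rating are also credited to W+, although the patient had to remain under observation to reach that rating. Death ends both the stay and the ratings, which pushes the same way.

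The two totals mix time before OIWS, when they could act as risk factors, with time after it, when they could be consequences. Neither reading can be recovered from the total. At stake is the interpretation of two rows of a descriptive table: a longer stay in W+ could be taken to support the association cited in section 4.4.1 when part or all of it comes from unequal observation.

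**Working it through.** **The plan's own figure.** The plan gives no figure for this comparison. Its only size figure is 50 patients, from about 50 consenting of 88 eligible (50/88 = 56.8%), with no power calculation. At the 16.7% incidence quoted in the introduction, 50 × 0.167 = 8.4 W+ patients would be expected.

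**Mechanism.** Assume a constant 3% chance of a positive rating per rated day. P(ever positive) = 1 − 0.97^(number of ratings).
- 4 ICU ratings: 1 − 0.97^4 = 11.5%. With the ward rating: 1 − 0.97^5 = 14.1%.
- 14 ICU ratings, still in the ICU at the cap: 1 − 0.97^14 = 34.7%.

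**Simulation with OIWS never altering stay.**
- *Rules from the plan:* daily ratings from weaning to transfer, 14-day cap, one ward rating, W+ if ever positive, 50 patients.
- *Assumptions:* post-wean stay log-normal with median 3, 5 or 7 days (log-SD 0.7); pre-wean stay log-normal with median 6 days (log-SD 0.5, minimum 3); ever-OIWS 16.7% (the quoted incidence) or 40% (assumed).

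Gap in mean total ICU stay, W+ minus W-:

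| Daily risk | 16.7% ever-OIWS (median 3, 5, 7) | 40% ever-OIWS (median 3, 5, 7) |
|---|---|---|
| Constant | 1.5, 2.3, 2.6 days | 1.7, 2.5, 2.9 days |
| Falls by factor 0.7 per day | 0.4, 0.4, 0.5 | 0.5, 0.6, 0.5 |
| Falls by factor 0.3, or day 1 only | about 0 | about 0 |

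With constant risk, the W+ median is the longer one in 77–91% of simulated studies, and a nominal 5% Mann-Whitney test rejects in 12–31%. With factor 0.7 it rejects in about 5–8%. The plan names no test for stay; the test is used here only as a gauge.

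**Second set of inputs** (post-wean median 6 days, log-SD 0.6, constant 3%). Counting ICU ratings only, mean post-wean stay is 9.0 days in W+ and 6.7 to 6.8 in W-, a gap of 2.2 to 2.3 days. Adding the ward rating reduces it to 1.9 days. The mean pre-wean stay is about 6.85 days (13.35 − 6.50 in the median-5 run), so W- total stay is about 6.8 + 6.85 = 13.6 days and the gap is 1.9/13.6 = 14% of it. At 16.7% ever-OIWS and a factor of 0.8, the gap is about 0.6 days. A rerun at factor 0.8 with the first set of inputs gave 0.7 to 0.9 days at 16.7% and up to 1.0 at 40%.

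**Landmark check** (constant 3%, post-wean median 5 days). OIWS status is fixed at weaning day 1, 2 or 3, and remaining stay is compared among patients still in the ICU. W+ against W-: 5.98 v 5.95, 5.41 v 5.41 and 5.21 v 5.20 days. The ever/never split of the same data, without the ward rating, gives 9.14 v 6.42.

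**Patients available at a 72 h landmark** (second set of inputs, 88% still in the ICU): 50 × 0.88 = 44. At constant 3%, 44 × (1 − 0.97^3) = 44 × 0.087 = 3.8 W+. If 16.7% are ever positive and all have become so by then, 44 × 0.167 = 7.3 W+.

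Ventilation time was not simulated.

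**The case against.** A reader might infer that the table will show longer stays in W+ whether or not OIWS matters. The documents do not support that. They give no day-by-day risk, and the literature review says symptoms can begin within 12 hours of stopping opioids, which would favour early clustering and a small gap. This part of the objection stands: the bias is possible and its direction is clear, but its size is open. It does not remove the point. Daily ratings to day 14, resumption at repeat weaning episodes, and a ward visit meant to catch later OIWS (section 6.1) all presume that onset is not confined to the first day.

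Three further points have weight. Section 5.1.1 does not name stay or ventilation; their inclusion follows from their listing in 4.4.1. Ratings pause after a dose re-increase until the next wean, so rated days and ICU days are not identical. Ventilation may end well before ICU transfer, so the figures for stay do not carry over to it.

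The consequence is also limited. The objectives are symptoms and cortisol, section 5.1.2 covers only kappa and cortisol, and section 6.2 calls the analyses predominantly descriptive and concedes confounding. That lowers the weight of the point, but leaving out a p-value does not remove the bias from a descriptive difference.

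**Conclusion.** The point holds as a secondary one. Ever/never grouping combined with ratings that largely stop at ICU transfer makes W+ membership depend on stay, and nothing in the plan corrects for it. Under the assumed distributions, the spurious gap in stay runs from about 0 days (OIWS confined to the first rating days), through roughly 0.4–0.7 days and up to 1.0 with wider-spread stays (risk falling by a factor of 0.7–0.8 per day), to about 1.5–3 days (constant risk). The ward rating and the 14-day cap are included in these ranges. They rest on assumed stay distributions and an unknown risk pattern. For ventilation time the direction is the same to the extent that ventilation continues after weaning starts; its size is not known.

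Two stronger readings are not supported: that the primary symptom analysis is compromised by this, and that total stay must not be tabulated. Readers of a descriptive ICU cohort will reasonably expect the totals.

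**What to change.** In sections 4.4.1 and 5.1.1, make the compared characteristics ICU time and ventilation time from ICU admission to first wean. Section 4.4.1 already uses this cut for cumulative opioid dose and duration of opioid administration, and later ratings cannot change time that ended before they began.

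If total stay and total ventilation are still reported, show the number of DSM-5 days rated in each group beside them, and state that the totals cannot be read as a cause or an effect of OIWS.

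Any comparison of post-wean stay should use OIWS status fixed at a landmark, for example 72 h after weaning starts, among patients still in the ICU, and be labelled exploratory.

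The cost is mainly analysis wording, since admission, weaning and rating dates are needed for the study anyway; ventilation must be recorded so that it can be split at first wean. The landmark drops early leavers and would leave only about 4–7 W+ patients of 50 under the assumed inputs, so it can only be descriptive.
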